To date, reports on the clinical performance of ZAs remain controversial. Different abutment type seems to be associated with different risks, which can arise at any stage of therapy and greatly influence patient's satisfaction and quality of life. Although some clinical investigations affirmed excellent performance of ZAs with survival rate approaching 100%,^{21,22} unexpected and early catastrophic fractures of OPZAs and TPZAs with friction-fitted titanium inserts both have been reported.^{22,23} OPZAs were considered to be accompanied by higher risks of fracture, screw loosening and permanent damage due to stress concentrations, especially with internal implant connections. While TPZAs with friction-fitted titanium inserts seem to require higher machining accuracy and failure of the connection between the zirconia sleeve and titanium insert is a concern.^{21,24-26}

Even though technological progress in the field of metal-free materials has given rise to considerable improvements of these two types of abutment over the decades, there is still lack of clinical evidence for the use of two types ZAs.

Recent studies also showed that pro-inflammatory cytokines in peri-implant crevicular fluid (PICF) were significantly related to peri-implant diseases and further marginal bone loss.^{27,28} Tumor necrosis factor alpha (TNF- α) and interleukin-6 (IL-6) are pro-inflammatory cytokines that appear to have an important role in periodontal tissue destruction.^{29,30} It's necessary to quantitatively determine the concentrations of cytokines in PICF of OPZAs and TPZAs with friction-fitted titanium inserts as potential biomarkers for peri-implant disease diagnosis.

Thus, the investigators designed this randomized split-mouth clinical trial to evaluate the

clinical, radiological and immunological outcomes of OPZAs and TPZAs with friction-fitted titanium inserts in single implant crowns in aesthetic region. The primary outcome is prespecified as mechanical complication rates at 1-year follow-up.

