Eligible patients have two missing teeth, and they will be randomly assigned into two groups: OPZAs group (OG): restored with the OPZAs; TPZAs group (TG): restored with the TPZAs with friction-fitted titanium bases. The study is an open-label trial without blinding.

Outcomes

All the included patients will be recalled for clinical, radiological and immunological re-evaluations 1-year after the final crowns delivery. Survival rates, mechanical complication rates, bleeding on probing (BOP%), probing depth (PD), modified plaque index (mPI), marginal bone loss (MBL), concentrations of pro-inflammatory cytokines (TNF- α , IL-6) in peri-implant crevicular fluid (PICF), and pink esthetics score/white esthetics score (PES/ WES) will be recorded.

Survival rates.²⁵ The survival rate was defined as the percentage of success implants and remained crowns which never been replaced.

Mechanical complications rates. Veneer chipping, abutments or implants fracture, screw loosening or fracture and other mechanical complications will be recorded during the 1-year

follow-up.

Peri-implant conditions. The indicators of peri-implant conditions included bleeding on probing% (BOP%), pocket probing depth (PD) and modified plaque index (mPI).

Marginal bone loss (MBL).²⁶ Peri-apical radiographs with paralleling technique will be performed on the day of final restorations delivery and 1 year later. The implant length is used as calibration reference. The distance between restoration margin and the most coronal level of implant-bone contact will be recorded. The final result calculate as the mean value of mesial and distal sites. The alteration of the distance between baseline and 1-year follow-up is defined as the MBL.

Pro-inflammatory cytokines in peri-implant crevicular fluid (PICF). The investigators will collect the patients' PICF with the paper strip (PerioPaper Strips; Oraflow Inc., Smithtown, NY, USA) at 1-year follow-up to access differences in pro-inflammatory cytokines (IL-6 and TNF- α) between two groups. Enzyme-linked immunosorbent assay (ELISA) will be used to analyzed PICF and evaluated the concentrations of cytokines. The PICF collection method and cytokines determination referred to Christopher A. Barwacz et al (Figure 2).¹⁸

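### Marginal bone loss is measured from the restoration margin, so a remade crown or abutment with a different margin is recorded as bone change at that site, and the plan has no rule for such sites

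*Combined protocol and SAP*

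**What the plan says.** The MBL paragraph under Outcomes (2. METHOD/DESIGN) fixes the measurement in five statements:

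- Timing: "Peri-apical radiographs with paralleling technique will be performed on the day of final restorations delivery and 1 year later".
- Scale: "The implant length is used as calibration reference".
- Distance: "The distance between restoration margin and the most coronal level of implant-bone contact will be recorded".
- Averaging: "The final result calculate as the mean value of mesial and distal sites".
- Outcome: "The alteration of the distance between baseline and 1-year follow-up is defined as the MBL".

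The same section anticipates that restorations may not survive the year unchanged. On survival it says: "The survival rate was defined as the percentage of success implants and remained crowns which never been replaced". On mechanical complications it says: "Veneer chipping, abutments or implants fracture, screw loosening or fracture and other mechanical complications will be recorded during the 1-year" follow-up.

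The term restoration margin is not defined. No section says how MBL is obtained when a crown or abutment has been replaced between the two films: there is no new baseline film, no exclusion rule and no implant-level reference point. The Missing data section counts drop-outs as non-success. That rule suits a binary outcome and does not address a continuous measurement at a site still under follow-up.

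**The concern.** The upper end of the measured distance is a feature of the prosthesis, not of the implant. While the same restoration stays seated in the same position, that end is fixed and the change score reflects bone alone. Once a crown or abutment is remade with its margin at another height, the two films are measured from different starting points, and the difference enters MBL as apparent loss or gain.

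The affected sites are selected by what happened to the restoration after randomization. Leaving them in adds an error of unknown sign. Dropping them afterwards would remove sites on the basis of a post-randomization event. Since the plan is silent, that choice would be made after the data are seen. At stake is the interpretation of MBL, the only radiological outcome in the protocol.

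**Working it through.** The plan states no figure that can be reproduced here: no number of patients, no replacement rate and no standard deviation for MBL. The check is therefore algebra, followed by an illustration.

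**1. Decomposition.** Let P be the distance from restoration margin to implant platform, and B the distance from platform to the most coronal bone contact. The recorded distance is D = P + B. With 0 for delivery and 1 for the 1-year film:

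MBL = D1 − D0 = (B1 − B0) + (P1 − P0)

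The first term is true bone change. The second is zero if the margin has not moved and equals the margin shift if it has.

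**2. Do the plan's safeguards remove the second term?** Calibration by implant length corrects image scale, not the starting point. Averaging mesial and distal sites leaves a shift common to both sides fully in place.

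**3. One site** (assumed values). With true MBL 0 mm, a shift of +0.25, +0.5 or +1.0 mm is recorded as that much loss, and the same negative shift as that much gain. With true MBL 0.2 mm, a shift of −0.5 mm gives 0.2 − 0.5 = −0.3 mm, and +0.5 mm gives 0.2 + 0.5 = 0.7 mm.

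**4. Difference between arms.** Let r be the share of sites with a moved margin and s the mean shift. The false difference is r_OG × s_OG − r_TG × s_TG. Both r and s are assumptions, with s taken as same-sign and equal in the two arms:

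| Replaced, one arm vs other | s = 0.25 mm | s = 0.5 mm | s = 1.0 mm |
|---|---|---|---|
| 2% vs 0% | 0.005 | 0.01 | 0.02 |
| 5% vs 0% | 0.0125 | 0.025 | 0.05 |
| 10% vs 0% | 0.025 | 0.05 | 0.10 |
| 10% vs 5% | 0.0125 | 0.025 | 0.05 |
| 5% vs 5% | 0 | 0 | 0 |

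For scale, 2% is one site in 50 and 10% is one site in 10.

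**5. Random-sign shifts.** The expected mean bias is then zero, but spread increases. With an assumed true SD of 0.30 mm, the SD becomes √(0.30² + r × s²). At r = 2% and s = 0.25 mm it is 0.302 mm. At r = 10% it is 0.339 mm for s = 0.5 mm and 0.436 mm for s = 1.0 mm.

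**6. With an implant landmark.** MBL = B1 − B0. The margin term is absent, so the artefact is 0 mm whatever the replacement rate.

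**The case against.** Four counter-arguments deserve weight.

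*Most sites are unaffected.* This stands. The artefact is exactly zero wherever the margin stays put. Listed complications such as chipping away from the margin need not lead to a remake. A reader might infer that mechanical failures in general show up as false bone change; only those that end with the margin in a new position do.

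*The error need not favour either arm.* This also stands. A reader might infer that it is tied to treatment, because the Background says "OPZAs were considered to be accompanied by higher risks of fracture, screw loosening and permanent damage due to stress concentrations". But the same section raises failure of the sleeve-insert connection for the two-piece design, reports early fractures of both types and describes the evidence as controversial. The null hypothesis is no difference, and no replacement rates are given. The documents therefore do not support a predicted direction or size.

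*Every numerical input is assumed.* True. The Background also mentions some investigations with abutment survival close to 100%, which fits better with the low end of the illustrated range. The same-sign assumption has no support in the documents.

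*The landmark may have been meant as the implant-abutment junction.* If so, it nearly coincides with the implant shoulder and the problem largely disappears. The text does not say this, and the source cited for the method cannot be consulted here. The possibility lowers the likely impact but is itself a reason to name the landmark.

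What remains is the absence of any rule for sites whose restoration was replaced, in a plan that foresees replacement.

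**Conclusion.** The point holds in a limited form. As written, MBL equals true bone change only while the restoration margin keeps its position. At a site where a remade crown or abutment has a different margin, the whole shift is recorded as bone change, and the plan does not say how such a site is handled.

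The effect on the comparison of arms is between nothing and small: 0 mm with equal rates and equal shifts, or on average with random-sign shifts, and 0.005-0.10 mm under the one-sided, same-sign scenarios of 2-10% replaced and 0.25-1.0 mm shift. Those inputs are assumptions, not figures from the documents.

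A reader might infer that the trial's main result is compromised. It is not. The Background names mechanical complication rates as primary and the Outcomes section names success rates; MBL is neither, so this point leaves the primary comparison untouched. The case for acting rests on how cheaply the artefact can be removed, not on a demonstrated bias.

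**What to change.** In the MBL paragraph, replace the restoration margin with the implant shoulder (platform). On the same two radiographs, measure from the platform to the most coronal bone contact, mesially and distally, average the two, and define MBL as the change in that average from delivery to 1 year.

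The implant must already be visible on each film, because its length provides the calibration. No new film, visit or reader is needed; the only cost is re-measuring films already read. If the implant-abutment junction was meant all along, the edit merely clarifies the text.

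If the restoration margin is kept, the plan would instead need a new baseline radiograph at each replacement, a prespecified rule for analysing those sites, and a sensitivity analysis without them. That costs more and still makes the result depend on a post-randomization event. Neither option yields MBL where the implant itself is fractured or lost, so a sentence on those sites should be added in either case.

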2. METHOD/DESIGN

Overview

The present study is designed as a prospective, single-center, split-mouth, randomized controlled clinical trial. The investigators plan to recruit several adult patients who have two missing teeth in the maxillary anterior region and plan to be restored with two single implant crowns. The clinical component of the study will be initiated in Feb. 2019 at the Department of Oral and Maxillo-facial Implantology, Shanghai Ninth People's Hospital, Shanghai Jiao Tong University, China.

All patients received oral hygiene instruction and periodontal treatment before implant surgery.

The investigators will record the age, gender, physical health of all participants and they will meet the following inclusion criteria. Peri-apical radiographs with paralleling technique will be performed on the day of final restorations delivery. Clinical radiological and immunological re-evaluations will be performed at 1 year after the final crowns delivery.

Inclusion criteria

1) age \geq 18; 2) patients with two missing teeth in esthetic region and plan to be restored with two single implant crowns; 3) adjacent to natural teeth; 4) absence of oral mucosal disease and oral infection; 5) implants with conical connection (Nobel Active, Nobel Biocare® or NobelReplace Conical Connection, Nobel Biocare®); 6) patients with the willingness to participate in the present study.

Exclusion criteria

1)Heavy smokers (>10 cigarettes/day); 2) uncontrolled periodontitis (Full mouth plaque score $>20\%$, full mouth bleeding score $>25\%$, residual pocket depth $>5\text{mm}$); 3) with systematic diseases that may affect implant therapy, such as uncontrolled diabetes mellitus (Fasting blood-glucose $>7.2\text{mmol/L}$, Glycosylated hemoglobin $>7\%$), current intake of bisphosphonates (treatment for malignancy), pregnant(or plan to get pregnant), with history of radiation therapy in head and neck region.

Recruitment

Patients who have two missing teeth in the maxillary anterior region and plan to be restored

with two single implant crowns will be recruited at the Department of Oral and Maxillo-facial Implantology, Shanghai Ninth People's Hospital, Shanghai Jiao Tong University, China. Eligible patients will receive the study information and informed consent, and any patients who do not sign the consent will not be included in the study.

Allocation and blinding

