PES/WES.^{27,28} In this study, pink aesthetic score (PES) and white esthetic score (WES) will be applied for the objective esthetic assessment of the final restoration. The investigators will take patients' intraoral photos by the camera (D70, Nikon, Tokyo, Japan) at 1 year follow up. The aesthetic effect will be assessed by two specific dentists independently. They will asked to give scores for variables of PES (Mesial papilla, distal papilla, level of soft-tissue margin, soft-tissue contour, alveolar process and soft-tissue color and texture) and WES (Tooth form, tooth volume/outline, color, surface texture and transparency) with the 0-1-2 scoring system. Final

PES/WES is the sum of the two.

The primary outcome variable is presupposed to be the success rates. And the null hypothesis is that there is no significant difference regarding mechanical complication rates between two groups.

Statistical analysis

All statistical analyses will be performed using SAS software, version 9.4 (SAS Institute). Normal tests will be performed to know the normality of continuous data before appropriate ways of statistical description and analysis were chosen. Means, standard deviations (SD) and student's t test will be used for data in accordance with normal distribution. Medians, inter quartile range (IQR) and Wilcoxon Rank Sum test will be used for non-normally distributed data. Qualitative data will be described and analyzed by percentage and Chi-square Test. A two-sided *P* value of less than 0.05 will be considered to indicate statistical significance.

Missing data

Sample size calculation was performed accounting for possible loss to follow-up. Moreover, the investigators will account for the data not missing at random due to unbalanced loss to follow-up by handling drop-outs as nonsuccess using the intention-to-treat principle.

Ethical considerations

Ethical approval

All eligible patients will receive study information and informed consent, and any patients who do not sign the consent will not be included in the study.

Withdraw

All patients in this study will be informed that they have the right to withdraw at any time during the study, regardless of whether they withdraw or not, the treatment required by the patients will be accepted.

4. Discussion

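### Marginal bone loss is compared with independent-sample tests, so the comparison uses neither the split-mouth pairing nor the baseline bone level; the cost is precision, not bias

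*Combined protocol and SAP*

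**What the plan says.** In the protocol's METHOD/DESIGN section, under Outcomes, the films are scheduled as follows: "Peri-apical radiographs with paralleling technique will be performed on the day of final restorations delivery and 1 year later". The measurement is taken from the restoration: "The distance between restoration margin and the most coronal level of implant-bone contact will be recorded". Mesial and distal readings are averaged, and the outcome is the difference between the two time points: "The alteration of the distance between baseline and 1-year follow-up is defined as the MBL". The implant's length serves to calibrate the film.

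Under Statistical analysis, the rule for all continuous data is "Means, standard deviations (SD) and student's t test will be used for data in accordance with normal distribution", and otherwise "Medians, inter quartile range (IQR) and Wilcoxon Rank Sum test will be used for non-normally distributed data". The t test is not described as paired. Its stated alternative is the rank sum test, which is for independent samples, so the natural reading is an independent-sample comparison in both cases. No regression, mixed model, covariate or within-patient analysis is named, although the Overview describes a split-mouth trial with two implant sites per patient.

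MBL is not primary. The Background names mechanical complication rates and the Outcomes text names success rates; neither names MBL.

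**The concern.** MBL is the only tissue outcome for which a per-site baseline is scheduled, and the plan uses that baseline only to subtract it. Subtraction fixes the baseline coefficient at 1. Reading error in the first film then enters the change with opposite sign, and if sites with more bone at delivery lose more, change depends on the starting level. In a small trial, part of a chance difference in starting level between the two sets of sites then stays in the abutment comparison.

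The second point is simpler. Two sites in one mouth are likely to be correlated, and an independent-sample test ignores that. The abstract presents hard-tissue health as one of the questions the trial will inform, and MBL is its radiographic measure, so the precision of this comparison matters.

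**Working it through.** The documents state no sample size, SD, correlation or effect size, so there is no figure of the plan's to reproduce. Every input below is an assumption: 20 pairs throughout, with other inputs varied.

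**1. Is the change score biased?** No. With equal variances at both times and baseline-to-follow-up correlation ρ, an additive site difference cancels, and about −(1 − ρ) of a chance baseline difference remains: −0.5 at ρ = 0.5, −0.3 at 0.7, −0.1 at 0.9. In simulation the change-score estimate averaged about 0 under no effect. Its correlation with the chance baseline difference was about −0.48, −0.39 and −0.24.

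**2. Cost of ignoring the pairing.** Let c be the correlation of MBL between the two sites of a patient. The mean difference has variance 2σ²(1 − c)/n, but the independent-sample test uses 2σ²/n, so its standard error is too large by 1/√(1 − c): 1.20 at c = 0.3 and 1.41 at c = 0.5. In simulation its type I error was about 0.02 and 0.008 instead of 0.05. At a true difference of 0.6 SD its power was about 0.45, against 0.58 (c = 0.3) and 0.72 (c = 0.5) for the paired test.

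**3. Gain from the baseline covariate, given pairing.** Let r be the correlation between change and covariate. The variance ratio, adjusted over unadjusted, is about (1 − r²) × (n − 2)/(n − 3). At n = 20 the second factor is 18/17 = 1.059. Break-even is r² = 1/18, so |r| ≈ 0.24.

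To obtain r, take a between-site SD of bone level s_b, reading error SD s_e, true-change SD s_c, and a slope β of change on true level:

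- Var(change) = β²s_b² + s_c² + 2s_e²
- Var(covariate) = s_b² + s_e²
- Cov = βs_b² − s_e² if the covariate is the same reading that was subtracted; βs_b² if its error is independent

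Example with 0.3/0.2/0.2 mm and β = −0.3: Var(change) = 0.0081 + 0.04 + 0.08 = 0.1281; Var(covariate) = 0.13; Cov = −0.027 − 0.04 = −0.067. So r = −0.067/√(0.1281 × 0.13) = −0.52, and the ratio is (1 − 0.27) × 1.059 = 0.77. With independent error, r = −0.027/0.129 = −0.21 and the ratio is 1.01.

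| s_b / s_e / s_c (mm) | β | Ratio, same reading | Ratio, independent error |
|---|---|---|---|
| 0.3 / 0.2 / 0.2 | 0 | 0.95 | 1.06 |
| 0.3 / 0.2 / 0.2 | −0.3 | 0.77 | 1.01 |
| 0.3 / 0.2 / 0.2 | −0.5 | 0.65 | 0.94 |
| 0.5 / 0.1 / 0.3 | 0 | 1.06 | 1.06 |
| 0.5 / 0.1 / 0.3 | −0.3 | 0.84 | 0.89 |
| 0.5 / 0.1 / 0.3 | −0.5 | 0.63 | 0.69 |

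Simulation agreed to within about 0.01. These are two illustrative settings, not bounds.

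**4. Which baseline can be used?** The planned distance starts at the margin of the restoration already assigned to that site. If abutment type shifts the margin by δ at both times, the shift cancels in the change score, but adjustment for the margin-based distance adds a bias of about δ(1 − ρ). For δ = 0.5 SD that is 0.25, 0.15 and 0.05 SD at ρ = 0.5, 0.7 and 0.9; simulation gave 0.25, 0.16 and 0.05.

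**The case against.** The strongest reply is that nothing here is an error. Under within-patient randomisation the change score estimates the abutment effect without bias, and change score against covariate adjustment is an efficiency preference for an outcome that is not primary. That stands. A reader might infer that site differences in general contaminate the MBL comparison, or that the result would be systematically wrong. The documents do not support this: additive differences are subtracted out, and only the part correlated with change remains.

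A reader might also infer that a clean baseline bone level is already being recorded and merely ignored. It is not. The planned reading runs from the delivered restoration, so the fix needs a further reading on the same film. That reading shares only some of the subtracted reading's error, and the gain shrinks as the table shows. This also stands.

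Thirdly, the large gains require that higher bone loses more, which the documents neither state nor quantify. Without it, the covariate could cost a little or gain a little. That stands too, and is why the adjusted result should appear beside the unadjusted paired result.

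The reply does not reach the pairing. Independent-sample tests in a split-mouth design discard information, whatever is decided about the baseline. Nor should the unpaired test be read as producing false positives: with positive between-site correlation it is conservative.

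**Conclusion.** The point holds as a matter of precision. As written, the MBL comparison uses neither the pairing nor the baseline level. The firmer loss is the pairing: at an assumed 20 pairs, between-site correlation of 0.3 to 0.5 and a 0.6 SD difference, power is about 0.45 where 0.58 to 0.72 was available. The covariate's contribution is uncertain, from about a 6% variance increase if change is unrelated to baseline to about a 37% reduction if higher bone clearly loses more, and it is smaller when the covariate's reading error is independent of the subtracted reading. If baseline and follow-up correlate at 0.9 with equal variances, the theoretical reduction of 5% is cancelled at 20 pairs by the cost of estimating the slope. The primary conclusion is unaffected. This is a low-cost improvement, not a flaw that invalidates the analysis.

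**What to change.** In the Statistical analysis section, state that MBL is analysed within patient. Regress the within-patient MBL difference (one abutment type minus the other) on the within-patient difference in delivery-day bone level; the intercept is the abutment effect. Report it with a 95% CI beside the unadjusted paired difference. If a mixed model with patient as random effect is preferred, split the baseline into within-patient and between-patient parts; otherwise the model also draws on between-patient baseline information and is not equivalent to the regression.

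Under Outcomes, keep the MBL definition, and add that the baseline covariate is read from a fixed point on the implant on the existing delivery-day film, not from the restoration margin. Fix this before any outcome data are seen, since the trial is open-label.

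The cost is analysis wording, one extra reading per existing delivery-day film, and one degree of freedom for the covariate (about 6% of variance at 20 pairs if the baseline proves uninformative). Pairing itself reduces the degrees of freedom from 38 to 19 at 20 pairs. No visit, film or procedure is added.

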Jiao Tong University School of Medicine

Clinical Research Protocol

Project Name: Evaluation of the one-piece zirconia abutments and two-piece zirconia abutments with titanium bases for single implant crowns in esthetic region: a randomized split-mouth clinical trial with 1-year follow-up

Version Number: V 2.0

Version Date: 2020/12/10

Project Manager: [name]

Start and End Dates: 2020/12 – 2022/12

PROTOCOL TITLE:

Evaluation of the one-piece zirconia abutments and two-piece zirconia abutments with titanium bases for single implant crowns in esthetic region: a randomized split-mouth clinical trial with 1-year follow-up

Abstract

Objective: To evaluate the clinical, radiological and immunological outcomes of the one-piece zirconia abutments (OPZAs) and two-piece zirconia abutments (TPZAs) with friction-fitted titanium bases in single implant crowns in aesthetic region.

Materials and methods: The study is a single center, split-mouth and randomized controlled clinical trial. Eligible patients will be randomly assigned into two groups: OPZAs group (OG) and TPZAs group (TG). Survival rates, mechanical complication rates, bleeding on probing (BOP%), probing depth (PD), modified plaque index (mPI), marginal bone loss (MBL), concentrations of pro-inflammatory cytokines (TNF- α , IL-6) in peri-implant crevicular fluid (PICF), and pink esthetics score/white esthetics score (PES/ WES) will be evaluated.

Discussion: Results of the present study will help to evaluate the clinical, radiological and immunological outcomes of OPZAs and TPZAs with friction-fitted titanium bases in single implant crowns in aesthetic region and provide evidence for the effects of two types abutments on the health of peri-implant soft and hard tissue.

Keywords: zirconia abutment, one-piece, two-piece, peri-implant crvicular fluid, inflammatory factors, peri-implant diseases

1. Background

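### The aesthetic outcome is planned as one undefined sum, with no separate comparison of PES or WES; both should be compared beside the total, with paired tests

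*Combined protocol and SAP*

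**What the plan says.** The PES/WES paragraph under Outcomes (2. METHOD/DESIGN) introduces two scores: "pink aesthetic score (PES) and white esthetic score (WES) will be applied for the objective esthetic assessment of the final restoration". On raters it says: "The aesthetic effect will be assessed by two specific dentists independently". The soft-tissue items are given as "PES (Mesial papilla, distal papilla, level of soft-tissue margin, soft-tissue contour, alveolar process and soft-tissue color and texture". The crown items and the scale for every item come next: "WES (Tooth form, tooth volume/outline, color, surface texture and transparency) with the 0-1-2 scoring system". The paragraph ends with the only rule for the endpoint: the final "PES/WES is the sum of the two".

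The text does not say whether *the two* means the two scores or the two dentists. No other sentence says how the dentists' scores are combined.

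The outcome list at the start of Outcomes treats the pair as one entry: "pink esthetics score/white esthetics score (PES/ WES) will be recorded". The Statistical analysis section names Student's t test, not stated to be paired, for normally distributed data and the Wilcoxon rank sum test otherwise. It names no analysis of PES or WES on its own.

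The Discussion paragraph of the Abstract says the results will "provide evidence for the effects of two types abutments on the health of peri-implant soft and hard tissue". The Background states: "The primary outcome is prespecified as mechanical complication rates at 1-year follow-up". The Outcomes section later names success rates as primary. On neither statement is PES/WES the primary outcome.

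**The concern.** PES describes the soft tissue around the implant and WES describes the crown. If the abutments differ in only one of these, or in opposite directions, a comparison of the sum can miss it. If the sum does differ, the planned comparison does not show whether soft tissue or crown is responsible. Tissue effects are among the trial's stated interests, so a reader will want to know which component moved.

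Two smaller gaps go with this. The summing rule can be read in two ways, and either reading leaves something unstated: PES plus WES has no rule for combining raters, and dentist plus dentist has no rule for combining PES with WES. In addition, the tests named for continuous outcomes do not make explicit use of the within-patient pairing that the split-mouth design provides.

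**Working it through.** The documents give no number of patients, SD, correlation or effect size for PES/WES, so there is no planned figure to reproduce. Step 1 uses the documents only. Steps 2 and 3 are illustrations on stated assumptions.

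**1. Scale, read as PES plus WES.** Six PES items × 2 = 12 points and five WES items × 2 = 10 points, total 22. Crown share: 10/22 = 45%. If soft-tissue colour and texture are counted as two items, PES has a maximum of 14, the total is 24 and the share is 10/24 = 42%.

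**2. Effect on the sum relative to PES alone.** Work with within-patient differences between the two abutments. Let r = SD(WES difference)/SD(PES difference), ρ = their correlation, and c = WES effect divided by PES effect, in score points. Then

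standardised effect on the sum ÷ standardised effect on PES = (1 + c)/√(1 + r² + 2ρr).

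For an effect on PES only (c = 0), call this ratio f. The number of pairs needed rises by 1/f²:

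| r | ρ | f | pairs, multiple |
|---|---|---|---|
| 0.5 | 0 | 0.89 | 1.25 |
| 1 | 0 | 0.71 | 2.00 |
| 1 | 0.3 | 0.62 | 2.60 |
| 1 | 0.5 | 0.58 | 3.00 |
| 1.5 | 0 | 0.55 | 3.25 |
| 1.5 | 0.5 | 0.46 | 4.75 |

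A negative correlation shrinks the loss: r = 1 and ρ = −0.5 give 1 + 1 − 1 = 1, so f = 1 and nothing is lost.

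**3. Power in one example.** Assume a standardised PES effect of 0.5, two-sided 0.05, 80% power and a normal approximation. PES alone needs ((1.960 + 0.842)/0.5)² = 31.4, so 32 pairs, with achieved power Φ(√32 × 0.5 − 1.960) = 81%. With r = 1 and ρ = 0, the sum with c = 0 needs 2 × 31.4 = 62.8, so 63 pairs. Power on the sum with 32 pairs depends on c:

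| WES effect relative to PES (c) | standardised effect on the sum | power, 32 pairs |
|---|---|---|
| −1 (equal, opposite) | 0 | 5% |
| −0.5 | 0.18 | 17% |
| 0 | 0.35 | 52% |
| +0.5 | 0.53 | 85% |
| +1 (equal, same direction) | 0.71 | 98% |

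The sum beats PES alone once 1 + c > √2, that is, c above about 0.41 (r = 1, ρ = 0).

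**4. Read as dentist plus dentist.** The sum of two raters is exactly twice their mean. Mean difference and SD both double, so the t statistic is unchanged, and ranks are unchanged. Only the reported range moves: six-item PES would run to 2 × 12 = 24.

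**5. Pairing.** The split-mouth design places both abutments in the same patient. The rank sum test treats the two sets of scores as independent, and the t test is not stated to be paired. The matching procedures are the paired t test and the Wilcoxon signed-rank test on within-patient differences.

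**The case against.** The strongest defence is that the plan introduces PES and WES to assess the appearance of the final restoration as a whole, and for that purpose a pink-plus-white total is coherent. Soft-tissue health, the subject of the sentence in the Abstract, is a different matter from appearance and has its own endpoints: bleeding on probing, probing depth, plaque index and cytokines. This stands. It is a reason to keep the total and not to present PES as the trial's test of tissue health.

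Several stronger readings are tempting, and the documents do not support them.

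- A reader might infer that the soft-tissue information is lost. It is not: the dentists score the individual variables, so both indices can be recovered, and nothing in the plan forbids analysing them. The gap is in the planned comparison.
- A reader might infer that the crown items mostly add noise. The Background motivates ceramic abutments by the poor shade of titanium, and WES includes colour and transparency. One arm has a titanium base, so a WES effect is plausible.
- A reader might infer that the sum always weakens the test, or that twice the pairs is an estimate for this trial. It is one scenario; with effects in the same direction the sum can be the more powerful choice.
- A reader might infer that summing the dentists' scores damages the analysis. It only rescales the score.

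Separate comparisons also add to an already long list of outcomes with no stated multiplicity control. That is a real cost, taken up with the fix.

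**Conclusion.** The point holds in limited form. The plan reduces the aesthetic outcome to one sum, leaves its terms undefined and plans no separate comparison of PES or WES. Read as PES plus WES, 42% to 45% of the scale is crown appearance, so a soft-tissue difference can be diluted or cancelled, or a difference in the total can go unattributed.

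Neither the direction nor the size of the consequence can be fixed from the documents. For an effect on PES only, over SD ratios of 0.5 to 1.5 and correlations of 0 to 0.5, the sum needs 1.25 to 4.75 times the pairs. For effects in the same direction it may need fewer. Read as a sum over dentists, there is no inferential consequence.

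This is a minor, inexpensive improvement to a secondary analysis. It does not affect the primary comparison.

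**What to change.** Make these changes to the PES/WES paragraph and the Statistical analysis section, before the scores are compared between groups:

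- State what is summed.
- State that each index is averaged over the two dentists.
- Compare PES and WES separately, alongside the PES + WES total and not in place of it.
- For each, use a paired t test or a Wilcoxon signed-rank test on within-patient differences.
- Label all of these comparisons as secondary and report all of them, whichever reaches significance.

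The cost is a few sentences and no new data, since the item scores are already to be collected. The price is one or two extra secondary comparisons. If the PES and WES tests were independent, the chance of at least one false positive at 0.05 would be 1 − 0.95² = 9.75%. With the total added, it is at most 3 × 0.05 = 15%. Stating the three comparisons in advance also removes the option of choosing among them after the results of an open-label trial are known.
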